## **1.2 Introduction to investigational treatment(s) and other study treatment(s)**

### **1.2.1 Overview of crizanlizumab (SEG101)**

Crizanlizumab is a selective IgG2 kappa humanized monoclonal antibody that binds to P-selectin with high affinity by blocking its interaction with its ligands, including P-selectin glycoprotein ligand 1 (PSGL-1). Extensive pre-clinical data have established P-selectin as a key mediator of VOC in SCD ([Matsui et al 2001](#)) and suggest that blockade of P-selectin could eliminate or reduce VOC.

The compound, crizanlizumab was initially developed by Reprivys Pharmaceuticals Corporation under the investigational drug code, SelG1. Novartis acquired the company on 18-Nov-2016, and is now the drug developer and sponsor for crizanlizumab, under the investigational drug code SEG101. On 15-November-2019 the US FDA approved

ADAKVEO® (crizanlizumab-tmca), for the reduction of the frequency of VOCs in adults and pediatric patients aged 16 years and older with sickle cell disease.

The approval was based on safety and efficacy data from the Phase II SUSTAIN study (Ataga et al 2017; see [Section 1.2.2](#)) below.

The crizanlizumab IB provides detailed information related to toxicology, non clinical pharmacology, drug properties, clinical and pre clinical data.

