### **3 Study design**

This is a multicenter, prospective, phase II, single-arm, open-label study to assess the efficacy and safety of crizanlizumab in SCD patients with priapism.

A total of approximately 36 male subjects aged  $\geq$  12 years, who meet all of the inclusion criteria and none of the exclusion criteria will be eligible for the study. Subjects with  $\geq$  4 priapic events during the 14 week pre-screening period and having at least 3 priapic events during the 12 week screening period with at least 1 event occurring within 4 weeks prior to the first treatment, will be included in the study.

The baseline period is defined as the 12 weeks screening period. Eligible subjects will be treated with crizanlizumab at a dose of 5.0 mg/kg. From the first screening visit until the end of follow-up, the total study duration will be up to 79 weeks (including 12 weeks of screening, 52 weeks of treatment and 15 weeks of follow-up as applicable). The primary analysis of the study will be conducted by 26 weeks to assess efficacy of crizanlizumab in those patient population, who have completed 26 weeks of treatment. The secondary [REDACTED] endpoints will be assessed by 26 weeks and/or 52 weeks. Subjects will be followed for safety for up to 105 days (15 weeks) after the last dosing if applicable. Subjects who will receive commercially approved

crizanlizumab approximately 4 weeks after their last dose of study treatment, do not need to complete the 105-day follow-up. The safety follow-up of these subjects will be at the End of Treatment (EOT) visit. All other subjects are required to complete the 105-day follow-up visit.

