## 6 Treatment

### 6.1 Study treatment

Novartis will supply crizanlizumab (SEG101) as an open-label medication. The investigational drug will be a crizanlizumab solution provided every 4 weeks with an additional loading dose 2 weeks after the first dosing (i.e. dosing on first day of Week 1, Week 3, Week 7, and then every 4 weeks until Week 51).

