## **9.2 Study completion and post-study treatment**

Study completion is defined as when the last subject finishes their Study Completion visit (defined as last patient last visit), and any repeat assessments associated with this visit have been documented and followed-up appropriately by the investigator, or in the event of an early study termination decision, the date of that decision. Subjects who will receive commercially approved crizanlizumab approximately 4 weeks after their last dose of study treatment, do not need to complete the 105-day follow-up. All other subjects are required to complete the 105-day follow-up.

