#### **10.1.4 SAE reporting**

To ensure subject safety, every SAE, regardless of causality, occurring after the subject has provided informed consent and until up to 105 days after the subject has stopped study treatment must be reported to Novartis within 24 hours of learning of its occurrence. Detailed instructions regarding the submission process and requirements are to be found in the investigator folder provided to each site.

All follow-up information for the SAE including information on complications, progression of the initial SAE and recurrent events must be reported as follow-up to the original event within 24 hours of the investigator receiving the follow-up information. An SAE occurring at a different time interval or otherwise considered completely unrelated to a previously reported one must be reported separately as a new event.

Any SAEs experienced after the end of the safety evaluation follow-up period should only be reported to Novartis if the investigator suspects a causal relationship to the study treatment.

Each re-occurrence, complication, or progression of the original event should be reported as a follow-up to that event regardless of when it occurs. The follow-up information should describe whether the event has resolved or continues, if and how it was treated, whether the blind was broken or not, and whether the subject continued or withdrew from study participation.

Follow-up information is submitted in the same way as the original SAE Report and should describe whether the event has resolved or continues, if and how it was treated, and whether the patient continued or withdrew from study participation.

If the SAE is not previously documented in the Investigator's Brochure or Package Insert (new occurrence) and is thought to be related to the study treatment, a Novartis Chief Medical Office and Patient Safety (CMO & PS) Department associate may urgently require further information from the investigator for health authority reporting. Novartis may need to issue an Investigator Notification (IN) to inform all investigators involved in any study with the same study treatment that this SAE has been reported.

Suspected Unexpected Serious Adverse Reactions (SUSARs) will be collected and reported to the competent authorities and relevant ethics committees in accordance with EU Guidance 2011/C 172/01 or as per national regulatory requirements in participating countries.

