Reduction: The negative change from baseline.

Study day: The study day, describes the day of the event or assessment date, relative to the start of study treatment. Study Day 1 for all assessments is taken to be the start of study treatment.

The study day is defined as:

- The date of the event (visit date, onset date of an event, assessment date etc.) - Start of study treatment + 1, if event is on or after the start of study treatment;
- The date of the event (visit date, onset date of an event, assessment date etc.) - Start of study treatment, if event precedes the start of study treatment.

The study day will be displayed in the data listings. If an event starts before start of study treatment, the study day displayed in the listing will be negative.

On-treatment assessment/event:

For AE reporting the overall observation period will be divided into three mutually exclusive segments:

1. Pre-treatment period: from day of subject's informed consent to the day before first dose of study medication
2. On-treatment period: from day of first dose of study medication to 105 days after last dose of study medication (or until EOT date for subjects continuing crizanlizumab after their EOT via commercial supply)
3. Post-treatment period: starting at Day 106 after last dose of study medication (or after EOT date for subjects continuing crizanlizumab after their EOT via commercial supply or a post-trial access program)

Note: If dates are incomplete in a way that clear assignment to pre-, on-, post-treatment period cannot be made, then the respective data will be assigned to the on-treatment period.

Safety summaries (tables, figures) include only data from the on-treatment period, unless specified otherwise, with the exception of baseline data which will also be summarized where appropriate (e.g., change from baseline summaries).

Time unit: A year length is defined as 365.25 days. A month length is 30.4375 days (365.25/12). If duration is reported in months, duration in days will be divided by 30.4375. If duration is reported in years, duration in days will be divided by 365.25.

Visit windows

Visit-windows will be applied for vital signs, laboratory and PRO assessments.

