2.4 Treatments (study treatment, rescue medication, concomitant therapies, compliance)

2.4.1 Study treatment / compliance

The Safety set will be used for the analyses below. Categorical data will be summarized as frequencies and percentages. For continuous data, n, mean, standard deviation (SD), lower quartile (Q1), median, upper quartile (Q3), minimum, and maximum will be presented.

The duration of exposure in weeks to study drug as well as the dose intensity (computed as the ratio of actual cumulative dose received and actual duration of exposure) and the relative dose intensity (computed as the ratio of dose intensity and planned dose intensity), will be summarized descriptively.

The number (%) of subjects with dose interruption or permanent discontinuation and the reasons will be summarized.

All dosing data will be listed.

Duration of exposure to study treatment

Duration of exposure to study treatment (week) = ((last date of exposure to study treatment) – (date of first administration of study treatment) + 1)/7.

The last date of exposure to study treatment the earliest of the last date of treatment + 27 days, the date of death (if the subject died), and the date of data cutoff.

Summary of duration of exposure of study treatment in appropriate time units will include categorical summaries (less than 1 weeks, at least 4 weeks, at least 14 weeks, at least 26 weeks, at least 52 weeks) and continuous summaries (i.e. mean, standard deviation (SD) etc.).

Cumulative dose

Cumulative dose of the study treatment is defined as the total dose given during the study treatment exposure and will be summarized.

The planned cumulative dose refers to the total planned dose as per the protocol up to the last date of investigational drug administration.

The actual cumulative dose refers to the total actual dose administered, over the duration for which the subject is on the study treatment as documented in the Dose Administration CRF.

Dose intensity and relative dose intensity

Dose Intensity (DI) for subjects with non-zero duration of exposure is defined as follows:

DI (mg/kg/28 days) = Actual Cumulative dose (mg/kg) / Duration of exposure to study treatment (week) × 4.

Planned dose intensity (PDI) is defined as follows:

PDI (mg/kg/28 days) = Planned Cumulative dose (mg/kg) / Duration of exposure (week) × 4.

Relative dose intensity (RDI) is defined as follows:

RDI = DI (mg/kg/28 days) / PDI (mg/kg/28 days).

DI and RDI will be summarized.

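### The on-treatment and post-treatment periods overlap for post-trial-access subjects, and for commercial switchers the adverse-event window closes nominally 13 days before counted exposure ends

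*SAP*

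**What the plan says.** SAP 2.1.1 and 2.7.1 and Protocol 12.6 give the same three safety periods and call them mutually exclusive. The on-treatment period ends 105 days after the last dose, with the exception "or until EOT date for subjects continuing crizanlizumab after their EOT via commercial supply". The post-treatment period begins on day 106, with a wider exception: "or after EOT date for subjects continuing crizanlizumab after their EOT via commercial supply or a post-trial access program". SAP 2.1.1 and 2.7 restrict safety summaries to on-treatment data.

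On exposure, SAP 2.4.1 says: "The last date of exposure to study treatment the earliest of the last date of treatment + 27 days", or death or data cutoff if earlier. It has no separate rule for subjects who continue on non-study drug.

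On follow-up, Protocol 9.2 provides that subjects who are to receive commercial crizanlizumab "approximately 4 weeks after their last dose of study treatment, do not need to complete the 105-day follow-up", and Protocol 3 adds: "The safety follow-up of these subjects will be at the End of Treatment (EOT) visit". Everyone else must complete the 105 days. Protocol 10.1.4, by contrast, covers every SAE from consent "until up to 105 days after the subject has stopped study treatment must be reported to Novartis within 24 hours" and does not mention switchers. Protocol 10.1.1 has the 105-day adverse-event window but qualifies it as applying where applicable. SAP 2.7.3 includes laboratory values up to 105 days after the last administration, with no exception.

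**The concern.** On-treatment status decides whether an event enters the safety tables or appears only as a flagged line in a listing. The boundary therefore has to be unique and has to agree with the other windows in the plan. Three things do not fit.

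- For a post-trial-access subject, the two exceptions give two different boundaries, and the programmer's choice of clause would settle the classification. The note in SAP 2.1.1 assigning unclear cases to the on-treatment period covers incomplete dates only.
- For a commercial switcher, the days between EOT and the planned first commercial dose follow study drug alone. The plan counts them as study exposure but leaves their events out of the on-treatment summaries.
- The shorter window for switchers was not carried through to SAE reporting or the laboratory summaries, so the duration of collection and summary depends on which section is read.

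**Working it through.** **Inputs.** Dosing is on the "dosing on first day of Week 1, Week 3, Week 7, and then every 4 weeks until Week 51" (Protocol 6.1). SAP Table 2-1 gives study day = (week − 1) × 7 + 1. EOT is last infusion + 2 weeks, ±7 days (Protocol 8), or within 14 days of the last dose after early discontinuation (Protocol 9.1.1). Exposure ends at last dose + 27 days (SAP 2.4.1). The planned commercial start is about 28 days after the last dose (Protocol 9.2). The standard on-treatment limit is 105 days.

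**Reproducing the plan's EoT day.** Week 51: (51 − 1) × 7 + 1 = 351. Week 53: (53 − 1) × 7 + 1 = 365. The difference is 14 days, which agrees with the Day 365 target in SAP Table 2-1 and with the protocol's two weeks.

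**Overlap for post-trial access.** The on-treatment period runs to day 105 after the last dose, because the exception does not name this route. The post-treatment period runs from the day after EOT, because its exception does. Days in both: 105 − 14 = 91. With EOT at +7 or +21 days: 98 or 84.

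**Exposure against the adverse-event window for commercial switchers.** Full-course exposure is 351 + 27 = 378 days (54.0 weeks).

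| EOT after last dose | Exposure days after EOT | Share of 378 days | Days to planned commercial dose |
|---|---|---|---|
| 7 | 27 − 7 = 20 | 5.3% | 28 − 7 = 21 |
| 14 | 27 − 14 = 13 | 3.4% | 28 − 14 = 14 |
| 21 | 27 − 21 = 6 | 1.6% | 28 − 21 = 7 |

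The mismatch is the second column; the fourth is a different quantity and is one day longer. All the mismatched days precede the planned commercial dose. The share is larger for shorter courses: with the last dose at Week 27 (day 183), exposure is 183 + 27 = 210 days and 13/210 = 6.2%. After early discontinuation EOT can fall at 0 to 14 days, which leaves 27 to 13 days.

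**EOT as a boundary.** SAP Table 2-1 lets the EoT analysis window run to day 447, on medical judgement and data. That is 447 − 351 = 96 days after a last dose on day 351, and 96 − 28 = 68 days past the planned commercial start. A delayed last infusion would shorten both, so this shows only that EOT may come late. If it came after the first commercial dose, the on-treatment period would take in time on commercial drug.

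**Windows for a commercial switcher, side by side.**

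| Item | Ends at | Source |
|---|---|---|
| Safety follow-up | EOT | Protocol 3; 105 days waived in 9.2 |
| On-treatment period | EOT | Protocol 12.6, SAP 2.1.1, 2.7.1 |
| Exposure | last dose + 27 days | SAP 2.4.1 |
| SAE reporting | up to 105 days | Protocol 10.1.4 |
| Laboratory summaries | 105 days | SAP 2.7.3 |

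**The case against.** The strongest reply is that ending follow-up at EOT for commercial switchers is a deliberate choice, made in Amendment 2 and repeated in Protocol 3, 9.2, 12.6 and Table 8-1 and in the SAP. Once commercial drug starts, later events cannot be ascribed to study supply alone. An exposure convention of one dosing interval and an adverse-event risk window also serve different purposes; they differ for non-switchers too (27 against 105 days). This stands as a defence of truncation. It does not explain two exceptions that disagree within one definition, or excluding days that precede any commercial dose.

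Several stronger readings are tempting but not supported:

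- A reader might infer that event rates are diluted. SAP 2.7.1 reports numbers and percentages of subjects, with no exposure denominator. The extra days enter exposure duration and dose intensity; in relative dose intensity the duration cancels.
- A reader might infer that events after EOT are lost. Protocol 10.1.4, as written, still covers SAEs to 105 days and causally suspected ones beyond. SAP 2.7.1 lists and flags post-treatment events, and SAP 2.7.2 summarizes post-treatment deaths. New non-serious events are the ones most likely to be missed.
- A reader might infer that a subject whose switch fails has no follow-up. The SAP clause concerns subjects who continue the drug, and Protocol 9.2 holds all others to 105 days. Difficulty can arise only if a planned start falls through after EOT.
- A reader might infer that post-trial-access subjects exist. Outside the period definition the documents describe no such program.

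**Conclusion.** The defect is one of definition and alignment, and its numerical size is modest. The overlap is certain from the text (about 91 days, 84 to 98) but may affect no one. The exposure mismatch is nominally 13 days per commercial switcher (6 to 20), or 3.4% of a full course. It assumes the scheduled EOT and a commercial start at about 28 days; the number of switchers is not given. The 105-day SAE and laboratory windows do not agree with the EOT cut for switchers. The point still merits correction because these rules decide which events are tabulated and the remedy is nearly free. The documents do not support a claim of materially biased incidence or wholesale loss of safety data.

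**What to change.** 1. In SAP 2.1.1, SAP 2.7.1 and Protocol 12.6, use identical wording and one end date in the on-treatment and post-treatment exceptions, covering both commercial supply and post-trial access. The overlap then falls from about 91 days to 0.
2. For these subjects, end the on-treatment analysis period on the day before the first non-study dose, and record that date. At the planned four weeks this is last dose + 27 days (day 378 for a full course), which equals the exposure end in SAP 2.4.1. State that the 105-day analysis window applies if no such dose is given.
3. Reconcile Protocol 3, 9.2, 10.1.1 and 10.1.4 and SAP 2.7.3 on how long adverse events, SAEs and laboratory data are collected and summarized for switchers. Step 2 can tabulate only events that are recorded, so the reconciled text must say what is collected between EOT and the first non-study dose.

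The cost is wording, one recorded date per switching subject, and slightly higher on-treatment event counts.

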Visit-windows will be used for the data that is summarized by visit; they are based on the study evaluation schedule and comprise a set of days around the nominal visit day. For any assessment, there are the protocol defined scheduled visits around which visit windows were created to cover the complete range of days within the study. The visit windows are shown in Table 2-1. These apply to measurements taken at every visit.

When visit windows are used, all visits will be re-aligned, i.e., they will be mapped into one of the visit windows (e.g., if the Week 4 visit of a subject is delayed and occurs on Day 46 instead of on Day 29, say, it will be re-aligned to visit window Week 8). In the case of major deviations from the visit schedule, or due to unscheduled visits, several assessments of a subject may fall in a particular visit window (either scheduled or unscheduled). Statistical approaches to handle multiple assessments in a given visit window are specified below.

Table 2-1 Assessment windows for scheduled visits

Analysis Visit	Week (k)	Scheduled Day/ Target day [d=(k-1)*7+1]	Visit Window (in study days)
Baseline	BSL		-91 days to Day -1*
Week 1 Day 1	1	1	Day 1-7
Week 3 Day 1	3	15	Day 8-29
Week 7 Day 1	7	43	Day 30-57
Week 11 Day 1	11	71	Day 58-85
Week 15 Day 1	15	99	Day 86-113
Week 19 Day 1	19	127	Day 114-141
Week 23 Day 1	23	155	Day 142-169
Week 27 Day 1	27	183	Day 170-197
Week 31 Day 1	31	211	Day 198-225
Week 35 Day 1	35	239	Day 226-253
Week 39 Day 1	39	267	Day 254-281
Week 43 Day 1	43	295	Day 282-309
Week 47 Day 1	47	323	Day 310-337
Week 51 Day 1	51	351	Day 338-358
EoT	53	365	Day 359-371**

*Baseline measurement prior to first infusion of study drug.

**Based on medical judgement and data, upper limit of EoT will be extended upto maximum value day 447.

Laboratory assessments will be taken from Screening Visit 3 as per the protocol and the window does not include pre-screening period. Thus, window for laboratory assessments will be Day - 28 to Day -1.

Multiple assessments within visit windows

In order to summarize laboratory assessments over time (including unscheduled visits), the assessments will be time slotted. The following general rule will be applied:

- If more than one assessment is done within the same time window, the assessment performed closest to the target date will be used.
- If 2 assessments within a time window are equidistant from the target date, then the earlier of the 2 assessments will be used.

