2.7.3 Laboratory data

On analyzing laboratory values, data from all sources (central and local laboratories) will be combined as per Section 8.3.2 of the protocol. The summaries will include all assessments available for the lab parameter collected no later than 105 days after the last study treatment administration date. Following lab parameters will be analyzed :

Table 2-1

Test category	Test name
Hematology	Hematocrit, Hemoglobin, MCH, MCHC, MCV, reticulocytes (%), Platelets, Red blood cells, White blood cells, RBC Morphology, Differential (Basophils, Eosinophils, Lymphocytes, Monocytes, Neutrophils, Bands, Other
Chemistry	Alkaline phosphatase, ALT, AST, Gamma-glutamyl transferase (GGT), Lactate dehydrogenase (LDH), Bicarbonate, Calcium, Magnesium, Phosphorus, Chloride, Sodium, Potassium, Creatinine, Creatine kinase, Direct Bilirubin, Indirect Bilirubin, Total Bilirubin, Total Cholesterol, LDL, HDL, Total Protein, Triglycerides, Blood Urea Nitrogen (BUN) or Urea, Uric Acid, Amylase, Lipase, Glucose (non-fasting), estimated glomerular filtration rate (eGFR).
Urinalysis	Macroscopic Panel (Dipstick), done locally: Color, Bilirubin, Blood, Glucose, Ketones, Leukocytes esterase, Nitrite, pH, Protein, Specific Gravity, Urobilinogen Microscopic Panel (performed if dipstick is positive): Red Blood Cells, White Blood Cells, Casts, Crystals, Bacteria, Epithelial cells Urine creatinine/protein ratio, Microalbumin
Coagulation	Prothrombin time (PT) , International normalized ratio [INR]), Activated partial thromboplastin time (APTT)
Hepatitis markers	HBV-DNA, HbsAg, HbsAb, HbcAb, HCV RNA-PCR, HCV Ab
Additional tests	HIV Ab

For results reported by the central laboratory, continuous hematology and chemistry results will be summarized descriptively in SI units at each scheduled time point. Visits summaries will include baseline and post baseline visits, including early termination and Follow-Up. Changes from baseline will also be summarized at each time point.

The following summaries will be produced for laboratory data by laboratory parameters:

Separate summaries of change from baseline for each lab test category.

- Worst post-baseline CTCAE grade (regardless of the baseline status). Each subject will be counted only once for the worst grade observed post-baseline.

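### The EoT laboratory row is filled by study day, but EOT is timed from the last infusion, so early stoppers' in-window EOT samples never reach that row

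*SAP*

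**What the plan says.** **SAP 2.1.1.**
- Scope: "Visit-windows will be applied for vital signs, laboratory and PRO assessments".
- Mapping: "When visit windows are used, all visits will be re-aligned, i.e., they will be mapped into one of the visit windows". No exception is made for EOT or early termination. The stated aim is that "visit windows were created to cover the complete range of days within the study".
- Table 2-1 has one EoT row: Week 53, target Day 365, window Day 359 to 371. Its footnote reads "Based on medical judgement and data, upper limit of EoT will be extended upto maximum value day 447". The lower limit does not move.
- Competing samples: "If more than one assessment is done within the same time window, the assessment performed closest to the target date will be used". For ties: "If 2 assessments within a time window are equidistant from the target date, then the earlier of the 2 assessments will be used".

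**SAP 2.7.3.** By-visit laboratory reporting has this scope: "Visits summaries will include baseline and post baseline visits, including early termination and Follow-Up". Eligible samples are those "collected no later than 105 days after the last study treatment administration date".

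**Protocol.**
- Section 8 sets EOT at two weeks after the last infusion, 7 days either side (+7 to +21). It sets safety follow-up at 105 days after the last infusion, with up to 7 days' lateness allowed.
- Section 9.1.1 asks subjects who stop treatment to have EOT within 14 days of the last dose, and lets a regular visit serve as EOT if the decision is taken there. All EOT assessments in Table 8-1 are due, including hematology, chemistry, coagulation and urinalysis.

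**The concern.** The two documents use the same visit name with different clocks. In the protocol, EOT is a fixed interval after the last infusion. In SAP Table 2-1, EoT is a calendar position about one year after the first infusion. The two agree for a subject who receives the Week 51 infusion on time and not for one who stops earlier.

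As written, the by-visit EoT row therefore omits early stoppers' EOT samples, and for some of them can hold an off-drug follow-up sample instead. A reader looking there for laboratory values at the end of treatment would get an incomplete and partly mislabelled picture. SAP 2.7.3 shows the intention to report early termination and follow-up visits, but Table 2-1 gives the programmer nowhere to put them.

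**Working it through.** **Inputs.** Infusions at Weeks 1, 3, 7, then every 4 weeks to Week 51 (protocol Table 6-1); windows and target days from SAP Table 2-1; EOT and follow-up timing from protocol Sections 8 and 9.1.1.

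**The plan's own figure.** Target day = (week − 1) × 7 + 1. Week 51 gives 351 and Week 53 gives 365, which is 351 + 14. The midpoint of 351 and 365 is 358, so the EoT row opens on Day 359; 365 ± 6 gives 359 to 371. Table 2-1 reproduces, and its EoT row is built for a subject last dosed at Week 51.

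**Can an early stopper's EOT reach Day 359?**
- EOT at +14 needs a last infusion on or after Day 359 − 14 = 345.
- EOT at +21 needs one on or after Day 359 − 21 = 338.
- The last infusion before Week 51 is Week 47, Day 323. With the dose 7 days late and EOT at +21: 323 + 7 + 21 = 351.
- If the Week 51 visit, held 7 days late, serves as EOT: 351 + 7 = 358, one day short.

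So 13 of the 14 possible last infusions (Weeks 1 to 47) give no in-window route to the row.

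**Where does the sample go?** For each last infusion at Weeks 7 to 47, vary the infusion from 7 days early to 7 days late (15 values) and cross it with the EOT day. Assume one infusion-day sample, one EOT sample and no other sample in the row.

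| EOT timing | Combinations | Infusion-day sample used | EOT sample kept under a treatment week | Reaches EoT row |
|---|---|---|---|---|
| +7 to +14 | 15 × 8 = 120 | 72 closer + 4 ties = 76 | 16 closer + 28 in next row = 44 | 0 |
| +7 to +21 | 15 × 15 = 225 | 100 closer + 4 ties = 104 | 16 closer + 105 in next row = 121 | 0 |

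These are counts over a grid of dates, not probabilities.

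Example: last dose at Week 23 on Day 155, EOT on Day 169. Both days lie in the Week 23 window (142 to 169), and the Day 155 sample is on target, so the EOT value is not shown by visit. With EOT at +21 (Day 176) the value is kept, but in the Week 27 row (170 to 197).

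**Follow-up at +105 days, infusions on schedule.**
- Last dose at Weeks 1 to 35 (10 of 14): Days 106 to 344, in rows Week 15 to Week 51.
- Last dose at Weeks 39, 43, 47: 267 + 105 = 372, 295 + 105 = 400, 323 + 105 = 428. All lie beyond 371 and within 447, so they enter the EoT row only through the extension.
- Last dose at Week 51: 351 + 105 = 456, in no window.

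**Subjects affected.** 36 × 0.05 = 1.8, about 2, at the plan's dropout rate. If 20% is assumed instead, 36 × 0.20 = 7.2, about 7.

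**The case against.** Several points on the other side are sound and limit the finding.

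- *Most values are not necessarily lost.* A reader might infer that early stoppers' EOT values usually vanish. That holds for the tighter +7 to +14 timing (76 of 120) but not over the full +7 to +21 window, where more are kept (121) than displaced (104). Only the absence from the EoT row is constant.
- *The EoT row is not a completers-only row.* A reader might infer that it describes only subjects who reached Week 51. The documents do not support that. Follow-up samples after Weeks 39 to 47 can enter it, and protocol 9.1.1 asks discontinued subjects to return for scheduled assessments where possible, so one seen near Day 365 could also fill it.
- *The follow-up problem is narrow.* The 105-day limit in SAP 2.7.3 already excludes +106 to +112, which is 7 of the 8 allowed follow-up days. Subjects moving to commercial crizanlizumab need no 105-day visit. The follow-up counts above apply to a visit on exactly +105; a visit held early would also be eligible.
- *The urine protein/creatinine ratio.* A reader might infer that early stoppers drop out of its change summary. SAP 2.7.3 refers to the EoT visit, and SAP 2.7.4.1 uses the same term for ECG, which is not windowed. The recorded-visit reading is natural, so this is an ambiguity and not a shown error.
- *Windowing by study day is a legitimate choice*, because it keeps exposure comparable within a row. Programming detail also sits in table shells and dataset specifications that are not available here. Neither point supplies the rows that SAP 2.7.3 calls for, and the SAP's own rule remains explicit.

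**Conclusion.** The mismatch is real and minor. Under the SAP's stated rule, no in-window EOT laboratory sample after a last dose at Weeks 1 to 47 enters the EoT row. Whether it is displaced or relabelled depends on timing. The Day 447 extension can place a follow-up sample in that row for subjects last dosed at Weeks 39 to 47. Table 2-1 lacks the early termination and Follow-Up rows that SAP 2.7.3 implies.

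Only by-visit summaries of windowed safety data are affected, for about 2 of 36 subjects at 5% dropout. It would be wrong to read this as a threat to the efficacy result or to detection of laboratory toxicity: listings, worst-grade tables and shift tables do not depend on the EoT row, and neither does the primary endpoint.

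The conclusion assumes visits within protocol windows and the SAP text applied literally. A subject whose dosing slipped well beyond 7 days could be an exception.

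**What to change.** Change the SAP only.

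1. In 2.1.1, state that the EoT row contains only samples recorded at the EOT visit, including early termination, on any study day, and that these do not compete with non-EOT samples under the closest-to-target rule.
2. Assign samples recorded at the Follow-Up visit to a separate Follow-Up row in Table 2-1. Either let that row run to +112 days, matching the protocol's visit window, or state that it holds samples to +105 days only. Otherwise visits at +106 to +112 days stay excluded under the present limit with nothing to say so.
3. Apply study-day windows to the remaining samples only, and leave the Week 51 window open-ended so that late Week 51 samples keep a row. For example, with an infusion on Day 361 and EOT on Day 375, both now fall in EoT and the infusion sample wins (4 against 10 days from Day 365). After the change each has its own row.
4. Delete the Day 447 footnote, which is then unnecessary.
5. In 2.7.3, state that the urine ratio uses the recorded EOT visit.

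The cost is a short labelling rule, one table row, one open-ended window, one deleted footnote and one sentence. No new data and no protocol amendment are needed. The downside is that the EoT row will mix exposure durations, so it should carry a footnote saying so.
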